#### 5.4 STRATEGIES FOR RECRUITMENT AND RETENTION

Subjects will receive compensation for completion of the Day 45, Day 90, and Day 180 visits. Subject stipend amounts will be outlined in the site specific ICF and approved by the IRB prior to subject enrollment.

#### 5.5 PARTICIPANT WITHDRAWAL OR TERMINATION

##### 5.5.1 REASONS FOR WITHDRAWAL OR TERMINATION

All subjects have the right to withdraw at any point during the study without prejudice. The investigator can discontinue any subject, at any time, if medically necessary. Subjects must be discontinued from the investigation by the investigator at any time for any of the following reasons:

- Withdrawal of informed consent.
- Pregnancy (no further study-related procedures will be performed).
- Any AEs for which treatment continuation would constitute an unacceptably high risk for the subject.

The reason for subject's withdrawal should be documented on the appropriate study specific CRF.

##### 5.5.2 HANDLING OF WITHDRAWALS OR TERMINATION

The subject must undergo the recommended follow-up assessments specified for the last study visit unless contraindicated due to a medical condition. Withdrawn subjects will not be replaced.

Subjects who are discontinued from the study due to an AE(s) will be treated according to standard clinical practice and will be followed-up until the final study visit/safety visit as described in **Section 7.3**. All pertinent information concerning the AE will be documented on the appropriate study-specific CRF.

A subject may discontinue from the study at any time without any penalty or loss of benefits to which the subject is otherwise entitled. An Investigator may also discontinue a subject from the study without the subject's consent, if the Investigator feels it is in the best medical interest of the subject. The date and the reason for study withdrawal will be indicated on the Study Exit CRF.

#### 5.6 PREMATURE TERMINATION OR SUSPENSION OF THE STUDY OR A STUDY SITE

The study or a study site can be prematurely terminated or suspended by the sponsor. Reasons for termination of the study or a study site may include, but are not limited to, the following:

- Subject enrollment is unsatisfactory.

Apyx Medical Corporation

Protocol Number: APX-21-04

Effective Date: March 19, 2024

Revision No: 7.0

Title: Histological Evaluation of Human Skin Biopsies to Assess the Effects of Renuvion APR Treatment as an Adjunct Procedure in Facelift Surgery

- The risks and benefits of continuing the study have been reassessed, and the risks outweigh any potential benefits.
- The incidence of AEs constitutes a potential health hazard to the subjects.
- New scientific data do not justify a continuation of the study.
- The investigator or study site exhibit serious and/or persistent non-adherence to the protocol, the Declaration of Helsinki, EN ISO 14155, and/or applicable regulatory requirements.
- The sponsor decides to terminate the study at any time for any other reason.

Furthermore, the study may be prematurely ended if the regulatory authority or the IRB has decided to terminate or suspend approval for the study, the study site, or the investigator.

If the study is prematurely terminated or suspended for any reason, the investigator must inform the subjects and assure appropriate follow-up treatment. Within the timeframes noted in applicable regulations, the sponsor will promptly inform the investigators, study sites, the IRB, and regulatory authorities of the termination or suspension of the study, as well as provide reasons for the action.

## 6. STUDY DEVICE

FDA-cleared devices shipped for use in clinical investigations conform to the applicable general safety and performance requirements (GSPR) apart from the aspects covered by the clinical investigation and that, with regard to those aspects, every precaution is taken to protect the health and safety of the subjects. This includes, where appropriate, technical, and biological safety testing and pre-clinical evaluation as well as provisions in the field of occupational safety and accident prevention and taking into consideration the state of the art. Apyx Medical will provide devices for use with either the Apyx One Console or Ultimate Gen 2 generator in this clinical investigation.

### 6.1 PACKAGING & STORAGE

The sponsor will provide appropriate packaging and storage instructions to the study sites.

### 6.2 ACCOUNTABILITY

The investigator, or designee, must maintain an inventory record using the site-specific Device Disposition Form of study devices received, used for treatment, and returned to the Sponsor to ensure that the clinical study device will not be dispensed to any person who is not a subject under the terms and conditions set forth in this protocol. There will be 100% accountability for all clinical study devices. The clinical study site shall maintain all devices received for clinical trial use in a locked, limited access cabinet or room until the end of the study unless they are returned to Apyx while the study is being conducted, such as at the end of study treatments.

### 6.3 DEVICE MALFUNCTION/OBSERVATION

All malfunctions of, or defects of the delivery system will be reported to the Sponsor by the investigational sites. This will include situations where the delivery system did not perform as intended; user errors; study device/component being physically defective, including out of the box failure.

## 7. STUDY PROCEDURES AND SCHEDULE

 APYX™ MEDICAL Apyx Medical Corporation	
Protocol Number: APX-21-04	Effective Date: March 19, 2024 Revision No: 7.0
Title: Histological Evaluation of Human Skin Biopsies to Assess the Effects of Renuvion APR Treatment as an Adjunct Procedure in Facelift Surgery	

## 7.1 PRE-PROCEDURE

Study subjects will have verification of eligibility criteria, a brief general examination including medical history, and pre-procedure assessments as detailed below completed within 30 days prior to undergoing the study procedure. In response to the ongoing coronavirus disease (COVID-19) pandemic, preoperative testing can be completed at the Investigator's discretion. Pre-operative testing should be performed as close to the scheduled study procedure as feasible, but in time to get the results.

The following pre-treatment assessments will be performed:

- Brief medical history and physical examination per the Investigator's standard of care.
- Urine pregnancy test (for females of childbearing potential).
- Baseline imaging using the site's photography system.
- ASA Physical Status.

Medications the subject is taking upon study entry should also be documented on the Case Report Forms (CRF). All concomitant prescription medications taken during study participation will be recorded on the appropriate study specific CRF. For this protocol, a prescription medication is defined as a medication that can be prescribed only by a properly authorized/licensed clinician. Medications to be reported on the CRF and entered on the eCRF are concomitant prescription medications, over-the-counter medications, and non-prescription medications.

Medications used for analgesia and/or anesthesia should also be recorded as concomitant medication. To ensure the capture of the foregoing information on pre-existing conditions, sites should also be attentive to the need to document without limitation and whenever discovered: (1) all chronic, episodic or 'as needed' medications used before study enrollment; (2) prior episodic or 'as needed' therapeutic interventions, procedures, or hospitalizations; and (3) recent or planned surgical procedures.

## 7.2 STUDY PROCEDURE

The lower facelift surgery will be performed as per the investigator's standard clinical practice. The Renuvion APR System treatment will be performed using 4 treatment passes with settings of 80% and 1.5 LPM of helium flow with an activation speed of approximately 1-3cm/s. See **Section 4.3.4.1** for detailed instructions regarding collection, storage, and shipment of punch biopsy tissue samples. For all subjects the Renuvion APR System will be used in open surgery between the skin and SMAS on the neck, submentum, and lower facial skin flap. The mid/upper-face area will not be treated with Renuvion. A video or photograph of the face after the biopsies will be taken prior to Renuvion treatment to ensure proper location of punch biopsies at the D180 visit.

Procedure data and adverse events will be captured.

## 7.3 FOLLOW-UP PROCEDURES

### 7.3.1 IMMEDIATELY POST-PROCEDURE

Following the procedure, the research staff and the subject will care for the treated areas using the Post-Procedure Care Instructions per the Investigator's standard clinical practice.

### 7.3.2 POST-PROCEDURE CARE INSTRUCTIONS

Subjects will be asked to return to the study site at the following times post-procedure:

- 1 day
- 2(+1) days (optional)
- 7 (±3) days

Apyx Medical Corporation

Protocol Number: APX-21-04

Effective Date: March 19, 2024

Revision No: 7.0

Title: Histological Evaluation of Human Skin Biopsies to Assess the Effects of Renuvion APR Treatment as an Adjunct Procedure in Facelift Surgery

- 14 ( $\pm 3$ ) days
- 45 ( $\pm 7$ ) days
- 90 ( $\pm 10$ ) days
- 180 ( $\pm 15$ ) days

Post-procedure assessments and 2D photographic imaging will be performed during the follow-up visits. The same standardized photography views will be used throughout the study.

Due to the challenges of COVID-19, if a subject is unable to return to the office for an in-person visit, follow-up visits will be conducted virtually. If a visit is completed virtually, missing assessments such as photographs will be documented as a protocol deviation specifically noting COVID-19. Outside of photographs, study investigators and study staff will ensure all other assessments related to each follow-up visit are completed virtually if the visit is done virtually. For virtual visits, the investigator and/or study staff completing the visit and assessments will be identified on the case report form; as well, the manner in which the visit was completed will also be recorded (i.e. video call, phone call, etc.). Virtual visits should be done via video call if possible, to ensure subject identity. If a telephone call must be done, the investigator and/or study staff must positively identify the subject prior to conducting the virtual visit by requesting the subject to state their address and date of birth. Subjects will be strongly encouraged to come in (albeit safely) for their D180 visit; this visit is vitally important as this is the primary endpoint and photographic images are needed for many of the assessments. Only investigators and study staff who have been trained and delegated to conduct virtual visits as indicated on the delegation log may conduct virtual study visits.

Subjects may be seen for an unscheduled appointment at any time at investigator's discretion.

Apyx Medical Corporation

Protocol Number: APX-21-04

Effective Date: March 19, 2024

Revision No: 7.0

Title: Histological Evaluation of Human Skin Biopsies to Assess the Effects of Renuvion APR Treatment as an Adjunct Procedure in Facelift Surgery

TABLE 3: STUDY REQUIRED PROCEDURES

	Baseline/ Pre- Procedure Screening 	Procedure (Day 0)	Day 1	Day 2(Optional )	Day 7	Day 14	Day 45	Day 90	Day 180
				2-3 days	4-10 days	11-17 days	38-52 days	80-100 days	165-195 days
Informed Consent	X								
Assess Inclusion/Exclusion Criteria	X	X							
Urine Pregnancy Test 	X	X							
Medical History	X								
General Physical Exam	X								
Review Medications	X	X	X	X	X	X	X	X	X
2D Photographic Images 	X	X			X	X	X	X	X
Study Procedure		X							
Adverse Event Assessment		X	X	X	X	X	X	X	X
Healing Assessment			X	X	X	X	X	X	X
Punch Biopsy		X							X
Global Aesthetic Improvement Scale (GAIS) 							X	X	X
Patient Satisfaction Questionnaire (PSQ)									X

 Pre-procedure Screening assessments to take place within 30 days prior to undergoing the procedure.

 Up to two urine pregnancy tests must be obtained prior to study procedure for females with child-bearing potential (one at pre-procedure screening and one on the day of the procedure prior to the procedure if screening and procedure are not performed on the same day).

 Digital photographs will be taken and labeled. Standard positioning and lighting will be used for all photographs.

 To be complete by Investigator and study subject at day 45, 90, and 180 follow-up visits.

 To be complete by study subject at day 180 follow-up visit.

## 7.4 STUDY SCHEDULE

### 7.4.1 SCREENING

- Obtain informed consent of potential participant verified by signature on study informed consent form.
- Verify all preliminary/screening inclusion/exclusion criteria are met.

### 7.4.2 BASELINE ASSESSMENT (CAN BE COMBINED WITH SCREENING VISIT)

- Document medical history.
- Obtain pregnancy screen (if applicable).
- Perform baseline photography.
- Document concurrent medications.

### 7.4.3 TREATMENT VISIT

- Obtain pregnancy screen (if applicable) prior to study treatment.
- Perform pre-treatment biopsies
- Perform study treatment.
- Provide post-treatment instructions.

### 7.4.4 FOLLOW-UP

Subjects will be asked to return to the clinic for follow-up visits at 1, 2 (optional), 7, 14, 45, 90, and 180 days post-treatment. At all visits, subjects will be assessed for safety and adverse events, healing progress, and protocol deviations. Standardized images will be completed at Day 7, 45, 90, and 180. At 45, 90, and 180-days post procedure study outcome measures (GAIS) will be completed. At the 180-day follow-up appointment the subject will complete a PSQ and punch biopsies will be taken as described in **Section 4.3.4.1**; confirm only acute NSAID use (a maximum 2-3 doses allowed), if applicable, in the prior 2 weeks.

### 7.4.5 SAFETY ASSESSMENTS

Assess for adverse events immediately post-treatment and at all follow-up visits. Healing progress will be assessed at all follow-up visits.

### 7.4.6 UNSCHEDULED VISIT

Investigator may see subjects for visits in addition to the protocol defined follow-up visits at their discretion. Any unscheduled visit or examination should be documented in the subject's medical record and adverse event form (if applicable) stating the reason for the visit and any actions taken. The Sponsor should be notified of the unscheduled visit.

### 7.4.7 END OF STUDY (COMPLETION)

All subjects who have signed an Informed Consent Form will be considered enrolled in the study. Subjects who complete the study duration will be considered to have completed the study. The end of study will be defined as completion of all study visits by all enrolled subjects. If a device-related AE, SAE, or unanticipated serious device-

 APYX™ MEDICAL Apyx Medical Corporation	
Protocol Number: APX-21-04	Effective Date: March 19, 2024 Revision No: 7.0
Title: Histological Evaluation of Human Skin Biopsies to Assess the Effects of Renuvion APR Treatment as an Adjunct Procedure in Facelift Surgery	

related effect is ongoing at the final study visit, the subject will be followed until resolution, until the condition stabilizes, until the event is otherwise explained, or the subject is lost to follow-up.

A study closure visit may be conducted at the study site in order to review record retention requirements, device disposition requirements, etc., with site personnel. The Sponsor may choose to conduct the closure visit via telephone contact if appropriate.

## 8. ASSESSMENT OF SAFETY

### 8.1 SPECIFICATIONS OF SAFETY PARAMETERS

#### 8.1.1 DEFINITION OF AN EXPECTED TREATMENT EFFECT (ETE) AND AN ADVERSE EVENT (AE)

An expected treatment effect is defined as any typical treatment side-effect of Renuvion APR System of mild to moderate severity and lasting up to a typical maximum duration. An adverse event is defined as any new medical problem, or exacerbation of an existing problem, experienced by a subject while enrolled in the study, whether or not it is considered device-related by the investigator.

An **adverse event** (AE) is any untoward or unfavorable medical occurrence in a human subject, including any abnormal sign (for example, abnormal physical exam or laboratory finding), symptom, or disease temporally associated with the subject's participation in the research, whether or not considered related to the subject's participation in the research.

A preexisting condition (one that is present at the start of the study) will be recorded as an AE only if the frequency, intensity, or the character of the condition worsens during the study period. Neither the condition, hospitalization, prolonged hospitalization, nor surgery are reported as an AE in the following circumstances: hospitalization or prolonged hospitalization for diagnostic or elective surgical procedures for a preexisting condition. Surgery should not be reported as an outcome of an AE if the purpose of the surgery was elective or diagnostic and the outcome was uneventful.

All ETEs and AEs will be collected during the conduct of this trial.

#### 8.1.2 DEFINITION OF SERIOUS ADVERSE EVENT (SAE)

Each adverse event should be assessed for its seriousness. The definition below should be used for this assessment. Please note that the term serious adverse event is not synonymous with a "severe" adverse event, which may be used to describe the intensity of an event experienced by the subject. Please refer to **Section 8.2.1** for severity definitions.

An adverse event should be classified as serious if it meets any of the following criteria:

- a. Death
 

Death was an outcome of the adverse event.
- b. Life-threatening
 

The subject was at substantial risk of dying at the time of the adverse event or use or continued use of the device.

Apyx Medical Corporation

Protocol Number: APX-21-04

Effective Date: March 19, 2024

Revision No: 7.0

Title: Histological Evaluation of Human Skin Biopsies to Assess the Effects of Renuvion APR Treatment as an Adjunct Procedure in Facelift Surgery

c. Hospitalization (initial or prolonged)

Admission to the hospital or prolongation of hospitalization was a result of the adverse event.

d. Disability or Permanent Damage

The adverse event resulted in a substantial disruption of a person's ability to conduct normal life functions, i.e., the adverse event resulted in a significant, persistent or permanent change, impairment, damage or disruption in the patient's body function/structure, physical activities and/or quality of life.

e. Congenital Anomaly/Birth Defect

Exposure to a medical product prior to conception or during pregnancy may have resulted in an adverse outcome in the child.

f. Required Intervention to Prevent Permanent Impairment or Damage (Devices)

Medical or surgical intervention was necessary to preclude permanent impairment of a body function, or prevent permanent damage to a body structure, either situation suspected to be due to the use of a medical product.

g. Other Serious (Important Medical Events)

The event does not fit the other outcomes, but the event may jeopardize the subject and may require medical or surgical intervention (treatment) to prevent one of the other outcomes.

Non-serious adverse events are all events that do not meet the criteria for a "serious" adverse event.

### 8.1.3 DEFINITION OF UNANTICIPATED ADVERSE DEVICE EFFECTS (EVENTS)

An unanticipated adverse device effect is defined as "any serious adverse effect on health or safety, or any life-threatening problem, or death caused by, or associated with, a device; if that effect, problem, or death was not previously identified in nature, severity, or degree of incidence in the investigational plan, or application (including supplementary application), or any other unanticipated serious problem associated with a device that relates to the rights, safety, or welfare of subjects."

## 8.2 CLASSIFICATION OF AN EVENT

### 8.2.1 SEVERITY OF EVENT

Each adverse event should be assessed for its severity, or the intensity of an event experienced by the subject, using the following classifications:

- **Mild:** easily tolerated by the subject, causing minimal discomfort and not interfering with everyday activities. These events generally do not require treatment.
- **Moderate:** sufficiently discomforting to interfere with normal everyday activities. These events are usually relieved by simple therapeutic measures.
- **Severe:** prevents normal, everyday activities. These events may require systemic drug therapy or other medical treatment.

### 8.2.2 RELATIONSHIP TO THE CLINICAL STUDY DEVICE

The relationship to the study device and procedure will be evaluated together and determined by the investigator utilizing the following categories:

- **Not Related:** An event for which an alternative explanation is conclusively identified – e.g., concomitant drug(s), concomitant disease(s), and/or the relationship in time suggests that a causal relationship is highly unlikely.
- **Related:** The adverse event follows a reasonable temporal sequence related to treatment by the device and/or study procedure, follows a known or suspected response pattern and a plausible alternative etiology cannot be identified.
- **Undetermined:** The relation of the adverse event has some temporal relationship to the device and/or study procedure, is not clearly due to another condition and the involvement of the study device is unknown.

The relationship should be assessed using the categories presented in **Table 8.2.2-1**.

**TABLE 8.2.2-1. RELATIONSHIP BETWEEN ADVERSE EVENTS AND CLINICAL STUDY DEVICE**

Definite	Definite relationship exists between the device/procedure and an adverse event
Probably Related	A reasonable causal relationship between the device/procedure and an adverse event is more likely than not.
Possibly Related	A reasonable relationship exists between the device/procedure and an adverse event, but the causal relationship is unclear or lacking.
Not Likely Related	A temporal relationship exists between the device/procedure and an adverse event, but there is no reasonable causal relationship. For example, the adverse event occurs in a time frame, which makes a causal relationship to device treatment improbable.
Unrelated	No relationship between treatment with the device/procedure and the adverse event exists.

### 8.3 TIME PERIOD AND FREQUENCY FOR EVENT ASSESSMENT AND FOLLOW-UP

The occurrence of an AE or SAE may come to the attention of study personnel during a study visit or upon review by a study monitor. All ETEs and AEs will be captured on the appropriate CRF. Information to be collected includes event description, date of onset, clinician's assessment of seriousness and severity, relationship to study device/treatment (assessed only by those with the training and authority to make a determination), actions taken, and date of event resolution. All AEs occurring while on study must be documented appropriately regardless of relationship. All ETEs/AEs assessed as "not yet resolved" must continue to be followed via telephone contact, email or clinic visit every 7 days or sooner as per the physician's direction until event resolution or stabilization.

A pre-existing condition should not be reported as an adverse event unless there has been a substantial increase in severity or frequency of the problem that has not been attributed to natural history. Changes in the severity of an event will be documented to allow for a determination if the event should be re-categorized from an ETE to AE.

Safety evaluations for this study include an interview with the study subject at each follow-up visit by the Investigator or delegated study staff to elicit information about any medical occurrence that meets the definition of Adverse Event. This information will be documented in CRF without regard for cause or relation to device and/or procedure.

In addition, study subjects will be instructed in the Informed Consent Form, the site's standard of care post-procedure take-home instructions, and verbally by study staff to report all complications experienced post study

 APYX ™ MEDICAL Apyx Medical Corporation	
Protocol Number: APX-21-04	Effective Date: March 19, 2024 Revision No: 7.0
Title: Histological Evaluation of Human Skin Biopsies to Assess the Effects of Renuvion APR Treatment as an Adjunct Procedure in Facelift Surgery	

procedure to the site personnel as soon as they occur/are observed. Study staff will ensure that monitoring and management of all adverse events is prioritized. Subjects may be asked to come into the site at any time to assess adverse events.

Study investigators are provided liberty to mitigate adverse events as deemed necessary per IHC GCP Guidelines E6(R2)4.3.2 which states “During and following a subject’s participation in a trial, the investigator/institution should ensure that adequate medical care is provided to a subject for any adverse events related to the trial”.

Adverse event resolution dates will be determined by investigator using either in-person or remote (phone, video call, text, email, etc.) examinations or communication with the subject. To ensure the most accurate reporting of adverse event durations, investigators are instructed not to wait until scheduled office follow-up visits to assess resolution.

It is the Investigator’s responsibility to determine seriousness, severity, and relatedness of the Adverse Event to the device and procedure using the definitions in this protocol.

The PI will record all reportable events with start dates occurring any time after informed consent is obtained until 7 (for non-serious AEs) or 30 days (for SAEs) after the last day of study participation. At each study visit, the investigator will inquire about the occurrence of ETES/AEs/SAEs since the last visit. Events will be followed for outcome information until resolution or stabilization.

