## 4.3 STUDY OUTCOME MEASURES

1. Change in histology evaluation of biopsy tissue between the untreated portion of the face and the Renuvion treated portion at the D180 visit and compared to baseline.
2. Analysis of all adverse events through the D180 follow-up visit.
3. Analysis of bruising post-procedure.
4. Analysis of swelling post-procedure.
5. Healing profile.
6. Analysis of bleeding during surgery.
7. The Principal Investigator will complete a PGAIS assessing overall aesthetic improvement in the treatment area at day 45, 90, and 180 post-treatment.
8. The subject will complete a SGAIS assessing overall aesthetic improvement in the treatment area at day 45, 90, and 180 post-treatment.
9. The subject will complete a Patient Satisfaction Questionnaire (PSQ) at the 180-day follow-up visit.
10. Change in estimated biological skin age from baseline to D180.

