### 5.2 INCLUSION CRITERIA

Subjects must meet all of the following criteria for study enrollment:

- Male or female subjects, ages 18 – 75 years old.
- ASA Physical Status Classification System Class I and Class II subjects.
- Planning to undergo a lower facelift procedure, with or without a neck lift, at the investigator's site.
- Understands and accepts the obligation not to undergo any other procedures or treatments in the areas to be treated during study participation.
- Absence of physical conditions unacceptable to the investigator.
- Females of childbearing potential who are sexually active must be willing to use an approved method of birth control during study participation.
- Willing and able to comply with protocol requirements, including study-required images/photos, assessments/measurements, and returning for follow-up visits.
- Willing to release rights for the use of study photos, including in publication.
- Able to read, understand, sign, and date the informed consent.
- Able to communicate with the site via video and/or photographs, in the event of a virtual follow-up visit.

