## 8.4 REPORTING PROCEDURES

### 8.4.1 ADVERSE EVENT REPORTING

All Adverse Events (AEs) and Expected Treatment Effects (ETEs) observed by study subjects, investigators, or other study staff from first exposure to the study product through last study follow-up visit will be recorded. If a device-related AE, ETE, SAE, or unanticipated serious device related effect is ongoing at the final study visit, the subject will be followed until resolution, until the condition stabilizes, until the event is otherwise explained, or the subject is lost to follow-up. The investigator should make every effort to ensure that follow-up includes any supplemental investigations as may be indicated to elucidate, as completely as practical, the nature and/or causality of the AE or SAE. This may include unscheduled follow-up visits for AE assessment.

Study subjects will be instructed in the ICF, post-treatment take home instructions, and verbally by study staff to report all AEs to the clinical study staff. AE information will be collected throughout the duration of the study and recorded on CRFs.

Any new medical problem, or an exacerbation of an existing condition, reported from the time the informed consent form is signed must be followed until the last study visit after the last study treatment or until event resolution.

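### Section 8.3 screens out some worsenings of pre-existing conditions that the AE definition in 8.1.1 takes in, so Outcome 2 can have two different counts

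*Combined protocol and SAP*

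**What the plan says.** Section 8.1.1 defines an AE as "any new medical problem, or exacerbation of an existing problem, experienced by a subject while enrolled in the study", and this applies "whether or not it is considered device-related by the investigator". For a condition present at the start of the study, the same section says that it "will be recorded as an AE only if the frequency, intensity, or the character of the condition worsens during the study period". It makes an exception for elective or diagnostic hospitalization and surgery.

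Section 8.3 gives a second rule for the same situation. A pre-existing condition is not to be reported as an AE "unless there has been a substantial increase in severity or frequency of the problem that has not been attributed to natural history". The protocol does not define *substantial*.

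Section 8.4.1 returns to the broader wording: "Any new medical problem, or an exacerbation of an existing condition, reported from the time the informed consent form is signed must be followed".

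Outcome measure 2 in Section 4.3 is "Analysis of all adverse events through the D180 follow-up visit". Section 10.1 plans descriptive statistics only. Section 10.2 allows up to 10 treated subjects at up to three sites.

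**The concern.** An investigator who sees a known condition get worse has two instructions. Under 8.1.1 the question is whether it worsened. Under 8.3 the questions are whether the increase was large enough and whether natural history explains it. The second rule asks for a judgement of cause before the event becomes an AE. Section 8.2.2 assesses relatedness for adverse events, so a worsening screened out under 8.3 is never put through that assessment.

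What is at stake is the AE count itself. The study is single-arm and descriptive, so there is no control group against which a shortfall would show. If sites apply different sections, the pooled count mixes two definitions.

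**Working it through.** The plan states no AE rate, power or precision figure that bears on this point, so there is nothing of its own to reproduce. The check is a comparison of the texts and one division.

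**1. The rules side by side.**

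| Feature | 8.1.1 | 8.3 | 8.4.1 |
|---|---|---|---|
| Size of change | Any exacerbation or worsening | Substantial increase only (undefined) | Any exacerbation |
| Type of change | Frequency, intensity or character | Severity or frequency; character not listed | Not restricted |
| Cause | No filter; device-relatedness does not matter | Excluded if attributed to natural history | No filter |

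**2. Where the conflict rests.** The sentence on pre-existing conditions in 8.1.1 is worded as *only if*. Read strictly, it states a necessary condition and does not by itself say that every worsening must be recorded. The obligation comes from the AE definition in the same section, which takes in any exacerbation, and 8.4.1 agrees with it. The conflict is therefore mainly between 8.3 and the AE definition.

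**3. Direction.** An increase in severity or frequency that is substantial and not attributed to natural history is also a worsening in frequency or intensity. Every event that passes 8.3 therefore passes 8.1.1. The reverse fails in three cases: a worsening that is not substantial, a change in character only, and a worsening put down to natural history. Hence the count under 8.3 is less than or equal to the count under 8.1.1, and the discrepancy runs one way.

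**4. Can such events occur?** Section 5.2 admits "ASA Physical Status Classification System Class I and Class II subjects". Section 4.3.4.7 describes ASA II as mild systemic disease and gives well-controlled diabetes or hypertension and mild lung disease as examples. Follow-up is 180 days. Such events are possible, but the documents do not say how frequent they are.

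**5. Weight of one subject.** Take subject-level incidence as the number of treated subjects with at least one AE divided by the number treated, n. Let k be the number of subjects whose only AE falls between the two rules. The difference in incidence is k / n. With n = 10:

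- k = 0: 0 points
- k = 1: 1/10 = 10 points
- k = 2: 2/10 = 20 points
- k = 3: 3/10 = 30 points

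The values of k are illustrations. Because n is at most 10, 1/n is at least 10 points. A subject who has another AE changes the event count but not this incidence.

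**The case against.** Several points on the other side stand.

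- **The protocol leans towards 8.1.1.** It is the section that defines an AE, 8.4.1 matches it, and 8.3 tells investigators to classify seriousness, severity and relatedness using the protocol's definitions. This makes the 8.3 sentence the outlier. It does not resolve the conflict, because no precedence is stated and 8.3 is where a site would look for event-assessment instructions.
- **The events in the gap are mostly minor.** They are small, changes of character only, or attributed to natural history. The synopsis describes healthy subjects, and Section 5.3 excludes ASA III or higher and significant or uncontrolled conditions that may compromise the patient's health. Bruising, swelling, healing and bleeding are separate outcomes. No test or sample size depends on the count.
- **The wording is *reported*, not *recorded*.** Section 8.3 does not forbid writing the worsening down. But it concerns reporting as an adverse event, and the protocol has no category of AEs that are recorded and not reported.

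A reader might infer more than the texts support:

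- **That Outcome 2 already has two counts.** The counts differ only if at least one event falls between the rules.
- **That screened-out events are lost for good.** Section 14.1 requires progress notes on all significant observations, and Table 3 has medications reviewed at every visit, so a trace in the source is likely for any worsening of note. It would still not be in the AE data unless someone went back for it.
- **That 8.3 flatly contradicts itself.** Its interview paragraph says "This information will be documented in CRF without regard for cause or relation to device and/or procedure", but this covers occurrences that already meet the AE definition. A threshold could operate before it.
- **That a probability of divergence can be given.** That would need a rate of such worsenings, and the documents have none.

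**Conclusion.** The concern holds as an inconsistency in the current text with a one-directional effect on a named outcome. Section 8.3 as written leaves out worsenings that meet the protocol's own AE definition, and it does so ahead of relatedness. Outcome 2 can therefore be counted in two ways, and sites could differ.

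The size is bounded only per subject: at least 10 percentage points of subject-level AE incidence for each affected subject with no other AE. This assumes at most 10 treated subjects and treated subjects as the denominator. Section 10.1 specifies no particular AE summary, so incidence is used here as the natural one. The expected number of affected subjects is unknown and may be zero. The point is worth correcting because the AE summary is descriptive and the correction is small. It does not put any test or sample-size calculation at risk.

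**What to change.** Replace the pre-existing-condition sentence in 8.3 with the 8.1.1 rule: a pre-existing condition is an AE if its frequency, intensity or character worsens during the study, whatever the attributed cause. Keep the 8.1.1 exception for elective or diagnostic hospitalization and surgery. Have Outcome 2 refer to that single rule.

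Record attribution to the underlying disease under relatedness. Section 8.2.2 has no natural-history category. The nearest is Not Related, which names concomitant disease as an alternative explanation. Table 8.2.2-1 uses a different, five-level scale, so the CRF guidance should say which category takes these events.

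One threshold rule used throughout, with *substantial* defined, would also restore consistency. But it would mean narrowing the AE definition and 8.4.1 and would sit poorly with an outcome that covers all AEs.

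The cost is one sentence in 8.3 plus CRF instructions, handled under the amendment policy in Section 15.2. The downside is that a few more minor AEs are recorded, so the reported AE rate may look slightly less favourable.
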